8.2.2.5 Sample Size Calculations

A total sample size of 600 is considered sufficient to detect an average treatment difference of 0.13 in mean change in the QNPZ-8 scores from baseline, where the treatment difference is averaged over the 4, 8, and 12 month visits in the first year and annual visits thereafter, with a power of 80% at a 5% significance level. The difference of 0.13 in mean change in the QNPZ-8 scores would not be clinically meaningful for an individual participant but would be clinically meaningful for a participant group. Table 3 displays the sample sizes necessary under several scenarios. The sample size of 600 assumes a standard deviation of 0.7 for change in QNPZ-8 scores from baseline to any follow-up visit and is inflated by 10% to account for missed visits and loss to follow-up. With this sample size, a treatment difference of 0.1 would be detected with 58% power.

The sample size calculations were performed for a balanced design, assuming that the QNPZ-8 scores follow a longitudinal mixed model with exchangeable within-participant correlation structure and normally distributed random effects. The correlation structure implies that the between-participant standard deviations of change in QNPZ-8 scores from baseline to a given follow-up visit are equal through follow-up within each treatment group. For simplicity, the SD in Table 3 is expressed as standard deviation of change from baseline to any follow-up visit. The model used for the sample size calculations assumes that every participant completes the month-48 visit, as an approximation for the projected mean follow-up of 4.5 years in the main START study.

Table 3. Total Sample Size for Detecting Average Treatment Differences Between the Early and Deferred Groups in Mean Change in QNPZ-8 Scores from Baseline, Averaged over Months 4, 8, 12, 24, 36, and 48; power 80 %, significance level 5%

Difference Early vs. Deferred	Total N (N inflated by 10%)			
	SD=0.5	SD=0.6	SD = 0.65	SD = 0.7
$\Delta = 0.10$	474 (521)	682 (750)	798 (878)	926(1019)
$\Delta = 0.13$	282 (310)	404 (444)	474 (521)	550 (605)
$\Delta = 0.15$	212 (233)	304 (334)	356 (392)	414 (455)

The assumption of SD=0.7 for the standard deviation of the *change in QNPZ-8 scores* from baseline was based on the following considerations.

- a. In the SMART study, QNPZ-5 scores were obtained at baseline and month 6 for 258 participants. The QNPZ-5 scores were based on four of the QNPZ-8 tests, excluding the HVLTR, Semantic Verbal Fluency, and the WAIS-III Digit Symbol tests, plus the Timed Gait test. The standard deviation of change in QNPZ-5 scores (pooled across the two treatment groups) was 0.52, with a 95% confidence interval of 0.48 – 0.57. The value of SD=0.7 was chosen conservatively to guard against model misspecification, including misspecification of the within-participant correlation structure. Also, the somewhat different composition of the neuropsychological test battery compared to the QNPZ-5 may result in a different, possibly higher SD of change for the QNPZ-8.
- b. In a different study, four neuropsychological tests were administered at baseline and month 12, including the Grooved Pegboard, Finger Tapping, Timed Gait, and the Digit Symbol Modalities tests. QNPZ-4 scores were calculated from the standardized test results. The standard deviation of changes in QNPZ-4 scores from baseline to month 12 was 0.7, 95% confidence interval of 0.6 – 0.9 in 108 HIV-infected patients ([name], personal communication).

The protocol team will monitor the standard deviation of change in QNPZ-8 scores and the within-participant correlation structure, pooled across treatment groups. Sample size will be recalculated concurrently with the sample size recalculation for the main START study.

8.2.2.6 Sample Size, Enrollment and Site Selection

Enrollment and Site Selection

Enrollment into the Neurology substudy is planned to start concurrently with the main START study. The Neurology substudy aims to co-enroll participants from a limited number of sites and to co-enroll a high proportion of eligible participants at these sites. Limiting the number of participating sites makes it easier to standardize the administration of the neuropsychological tests and also is more cost effective.

It is planned to assess feasibility and re-calculate sample size for the Neurology substudy concurrently with the main START study, taking into account the observed standard deviation of change in QNPZ-8 scores and the expected duration of the main study.

8.2.2.7 Participant Selection

A total of 600 participants will be enrolled at selected sites that are geographically diverse and ensure a demographically diverse population. At these sites, it is planned to co-enroll a high proportion of the eligible START study participants.

Inclusion Criteria

- Simultaneous co-enrollment in the START study
- Signed informed consent (see Appendix A6)
- Age \geq 18 years

Exclusion Criteria

Participant is unable to perform necessary tests in the protocol, in the clinician's judgment.

8.2.3 Clinical Management Issues

8.2.3.1 Administration of the Neuropsychological Tests

The research staff who will administer the neuropsychological tests will be well trained in the standardized format in which these tests should be given. Research staff will participate in follow-up training to ensure correct administration of the tests as necessary. The tests are simple to administer and the total time per study visit will take about 50 minutes.

Table 4. Expected Time Needed for Tests and the CES-D

Test	Time
Grooved Pegboard (both hands)	8 min
Color Trails 1 and 2	3-8 min
WAIS-III Digit Symbol	5 min
HVLT-R, Learning	10 min
HVLT-R, Delayed Recall	3-5 min
Semantic Verbal Fluency	3 min
Finger Tapping (Both Hands)	8 min
CES-D	5 min
Total	45 - 52 min

The ethos that will underpin the training of the clinicians who will administer these tests is that the tests are serving as measures of the health of the participants' neurocognitive and motor performance. Thus, any discussions about these tests with the participants should impart the notion that we are seeking to define their neurocognitive health rather than their neurocognitive impairment.

All efforts will be made to make the participants feel comfortable and relaxed during the testing. If participants become fatigued or anxious during the testing they will be given an opportunity to rest and the testing may be ceased prematurely at the participant's request. During the administration of the tests, participants will be positively encouraged irrespective of their performance on the tests.

The test scores for the individual tests will be collected on standardized case report forms. The z-scores, ADS scores, and CES-D scores will be calculated at the INSIGHT statistical center. Calculated test scores will not be available in real-time, and will not be returned to the clinical sites. Participants in the Neurology substudy should continue to receive screening for cognitive impairment as per local standard of care. If concerns arise during the administration of tests or the CES-D questionnaire, it is recommended that participants be referred for diagnosis and treatment according to local guidelines.

8.2.3.2 Study Withdrawal

Participants may withdraw from the study at any time at their request, as described in section 4.5 of the START protocol. A participant can withdraw from the Neurology substudy and still be followed in the START study. If a participant withdraws from the main START study, the participant will be withdrawn from the Neurology substudy.

Otherwise, participants should be followed according to protocol, even if a participant chooses not to adhere to the treatment assignment or data collection schedule.

8.2.4 Evaluation

8.2.4.1 Data Analysis

All analyses comparing the treatment groups will be by intent to treat. Comparisons between treatment groups will be stratified by geographical area of enrollment, unless sample sizes are too small or stratification is inappropriate for other reasons.

Primary Analysis

For the primary objective, mean changes in QNPZ-8 scores from baseline will be compared between the early and deferred groups using all measurements through follow-up in a longitudinal mixed-effects model, stratified by geographical area of enrollment. The model will also include “month of visit” as categorical covariate, to adjust for a possible learning effect that would occur equally in both treatment groups.

Secondary Analyses

For each of the component tests of the QNPZ-8, mean changes from baseline in unadjusted test scores and in z-scores will be compared between the early and deferred groups using all measurements through follow-up in longitudinal mixed-effects models. The slopes in these endpoints through year 1 and through follow-up will also be compared between treatment groups, using longitudinal mixed-effects models.

Additionally to the standard longitudinal mixed-effects models that assume Gaussian distributions for the random effects, changes in tests scores through follow-up will be compared between treatment groups using O’Brien’s rank-sum test for multiple endpoints.⁸⁰ The two treatment groups will also be compared for changes in test scores from baseline to last visit, and for area under the curve from baseline through follow-up for the QNPZ-8 and each of the component tests.

The early and deferred ART arms will be compared for changes in test scores (QNPZ-8, z-scores, and unadjusted test scores) within subgroups of participants defined by demographics (age, sex, race/ethnicity, education, occupation, employment status, income, urban or rural area of residence), geographic location, CD4+ cell count, HIV RNA level, and other baseline characteristics using longitudinal mixed models. Presence of differential treatment effects across subgroups will be assessed by tests for interaction between subgroup and treatment group indicators in these longitudinal models.

In order to assess presence of a lateral effect on neurocognitive functioning, for finger tapping and grooved pegboard, the interaction between treatment group indicator and indicator for dominant versus non-dominant hand will be assessed in longitudinal models with double-repeated measures (within participant, measures are repeated over time, and across hands). If there is evidence for such an interaction, it will be investigated as to whether it changes over time, for example, by fitting an additional slope parameter. Change in test scores will also be compared between the dominant and non-dominant hands within the treatment groups.

The effect of classes of antiretroviral drugs on neurocognitive functioning will be assessed by comparing the early versus deferred ART treatment effect between subgroups of participants: those whose planned initial ART regimen (determined prior to randomization) contains the drug class under investigation, and those whose planned initial regimen does not contain the drug class. This means, the effect of the drug class will be assessed through the interaction effect between treatment and subgroup indicator. Also, ART regimens will be classified by their estimated level of CNS penetration. To test the hypothesis that higher CNS penetration protects neurocognitive functioning, the interaction effect between CNS penetration and treatment group indicator will be assessed in longitudinal models.

The early and deferred groups will be compared for proportions of participants with neurocognitive impairment using longitudinal models for binary data, for example, generalized estimating equations (GEE). The ADS is an alternative measure of neurocognitive impairment. The early and deferred groups will be compared for changes in ADS using longitudinal mixed models for ordinal data. Subgroup analyses will be performed if sample size is sufficient.

The association of changes in neuropsychological test scores with baseline factors and time-varying factors will be assessed by including these factors as independent variables in longitudinal mixed models. The association will be assessed within the early and deferred groups separately and also pooled across treatment groups if there is no evidence for differential opposite-treatment effects. Follow-up time spent at various levels of the time-varying factors will be tabulated to support the interpretation of the above analyses. For example, to help interpret the association of changes in neurocognitive functioning with the estimated CNS penetration levels of the ART regimens, the CNS penetration level will be included as a time-updated covariate in longitudinal models, and also exposure time to ART regimens of different CNS penetration levels (or no ART) will be tabulated.

Additionally, changes in test scores will be summarized through follow-up (e.g., as area under the curve), and linear regression methods will be used to investigate predictors that can be identified at baseline.

Linear regression methods will be used to assess the association of baseline factors with neuropsychological test scores at baseline in cross-sectional analyses.

Alcohol use, recreational drug use, and depression influence neurocognitive functioning. Alcohol use and recreational drug use (collected in the main START study), and depression scores will be tabulated through follow-up to provide supporting information for the treatment comparisons and to describe the substudy population. Baseline values will be assessed as explanatory factors for changes in neurocognitive functioning. Treatment groups will be compared for changes in CES-D scores using longitudinal mixed models.

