3.4 Randomization

Eligible participants will be randomized in a 1:1 ratio to either the early ART group or the deferred ART group. Randomization will be stratified by clinical site.

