8.2.2 Methodology**8.2.2.1 Study Design**

This is a substudy of START. It is planned to co-enroll a total of 600 participants over 3 years at selected, geographically diverse sites. Randomization (1:1 ratio) to the early or deferred treatment groups will be determined by the START study. Participants will be followed to the common closing date of START. This is estimated to be 6 years after the beginning of enrollment (3 years of enrollment and a minimum of 3 years follow-up for each participant). Before enrollment ends, sample size of the main START study will be re-assessed and sample size recalculated. At the same time, sample size for the Neurology substudy will be re-calculated.

START Neurology Substudy Schematic

Data collection: Baseline, months 4, 8, 12, and annually thereafter.

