8.2.2.5 Sample Size Calculations

A total sample size of 600 is considered sufficient to detect an average treatment difference of 0.13 in mean change in the QNPZ-8 scores from baseline, where the treatment difference is averaged over the 4, 8, and 12 month visits in the first year and annual visits thereafter, with a power of 80% at a 5% significance level. The difference of 0.13 in mean change in the QNPZ-8 scores would not be clinically meaningful for an individual participant but would be clinically meaningful for a participant group. Table 3 displays the sample sizes necessary under several scenarios. The sample size of 600 assumes a standard deviation of 0.7 for change in QNPZ-8 scores from baseline to any follow-up visit and is inflated by 10% to account for missed visits and loss to follow-up. With this sample size, a treatment difference of 0.1 would be detected with 58% power.

The sample size calculations were performed for a balanced design, assuming that the QNPZ-8 scores follow a longitudinal mixed model with exchangeable within-participant correlation structure and normally distributed random effects. The correlation structure implies that the between-participant standard deviations of change in QNPZ-8 scores from baseline to a given follow-up visit are equal through follow-up within each treatment group. For simplicity, the SD in Table 3 is expressed as standard deviation of change from baseline to any follow-up visit. The model used for the sample size calculations assumes that every participant completes the month-48 visit, as an approximation for the projected mean follow-up of 4.5 years in the main START study.

Table 3. Total Sample Size for Detecting Average Treatment Differences Between the Early and Deferred Groups in Mean Change in QNPZ-8 Scores from Baseline, Averaged over Months 4, 8, 12, 24, 36, and 48; power 80 %, significance level 5%

Difference Early vs. Deferred	Total N (N inflated by 10%)			
	SD=0.5	SD=0.6	SD = 0.65	SD = 0.7
$\Delta = 0.10$	474 (521)	682 (750)	798 (878)	926(1019)
$\Delta = 0.13$	282 (310)	404 (444)	474 (521)	550 (605)
$\Delta = 0.15$	212 (233)	304 (334)	356 (392)	414 (455)

The assumption of SD=0.7 for the standard deviation of the *change in QNPZ-8 scores* from baseline was based on the following considerations.

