8.2.2.6 Sample Size, Enrollment and Site Selection

Enrollment and Site Selection

Enrollment into the Neurology substudy is planned to start concurrently with the main START study. The Neurology substudy aims to co-enroll participants from a limited number of sites and to co-enroll a high proportion of eligible participants at these sites. Limiting the number of participating sites makes it easier to standardize the administration of the neuropsychological tests and also is more cost effective.

It is planned to assess feasibility and re-calculate sample size for the Neurology substudy concurrently with the main START study, taking into account the observed standard deviation of change in QNPZ-8 scores and the expected duration of the main study.

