8.2.2.7 Participant Selection

A total of 600 participants will be enrolled at selected sites that are geographically diverse and ensure a demographically diverse population. At these sites, it is planned to co-enroll a high proportion of the eligible START study participants.

Inclusion Criteria

- Simultaneous co-enrollment in the START study
- Signed informed consent (see [Appendix A6](#))
- Age \geq 18 years

Exclusion Criteria

Participant is unable to perform necessary tests in the protocol, in the clinician's judgment.

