8.2.4 Evaluation

8.2.4.1 Data Analysis

All analyses comparing the treatment groups will be by intent to treat. Comparisons between treatment groups will be stratified by geographical area of enrollment, unless sample sizes are too small or stratification is inappropriate for other reasons.

Primary Analysis

For the primary objective, mean changes in QNPZ-8 scores from baseline will be compared between the early and deferred groups using all measurements through follow-up in a longitudinal mixed-effects model, stratified by geographical area of enrollment. The model will also include “month of visit” as categorical covariate, to adjust for a possible learning effect that would occur equally in both treatment groups.

Secondary Analyses

For each of the component tests of the QNPZ-8, mean changes from baseline in unadjusted test scores and in z-scores will be compared between the early and deferred groups using all measurements through follow-up in longitudinal mixed-effects models. The slopes in these endpoints through year 1 and through follow-up will also be compared between treatment groups, using longitudinal mixed-effects models.

Additionally to the standard longitudinal mixed-effects models that assume Gaussian distributions for the random effects, changes in tests scores through follow-up will be compared between treatment groups using O’Brien’s rank-sum test for multiple endpoints.⁸⁶ The two treatment groups will also be compared for changes in test scores from baseline to last visit, and for area under the curve from baseline through follow-up for the QNPZ-8 and each of the component tests.

The early and deferred ART arms will be compared for changes in test scores (QNPZ-8, z-scores, and unadjusted test scores) within subgroups of participants defined by demographics (age, sex, race/ethnicity, education, occupation, employment status, income, urban or rural area of residence), geographic location, CD4+ cell count, HIV RNA level, and other baseline characteristics using longitudinal mixed models. Presence of differential treatment effects across subgroups will be assessed by tests for interaction between subgroup and treatment group indicators in these longitudinal models.

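### The Neurology substudy's primary QNPZ-8 model omits clinical site, the factor START randomises within, so its interval is slightly conservative; a random site intercept is a free improvement

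*Supplement*

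**What the plan says.** The references are to protocol Version 2.0.

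- Allocation, section 3.4: "Randomization will be stratified by clinical site". Section 8.2.2.1 adds: "Randomization (1:1 ratio) to the early or deferred treatment groups will be determined by the START study". An inclusion criterion in section 8.2.2.7 is "Simultaneous co-enrollment in the START study".
- Primary analysis, section 8.2.4.1: changes in QNPZ-8 are compared "in a longitudinal mixed-effects model, stratified by geographical area of enrollment". Month of visit also enters, "as categorical covariate, to adjust for a possible learning effect that would occur equally in both treatment groups". No site term, fixed or random, is named.
- Other treatment comparisons, same section: these are to be "stratified by geographical area of enrollment, unless sample sizes are too small or stratification is inappropriate for other reasons".
- Sites, section 8.2.2.6: their number is to be limited, partly because "Limiting the number of participating sites makes it easier to standardize the administration of the neuropsychological tests". The number itself is not given.
- Sample size, section 8.2.2.5: "A total sample size of 600 is considered sufficient to detect an average treatment difference of 0.13 in mean change in the QNPZ-8 scores", with 80% power at the 5% level, an SD of change of 0.7, exchangeable correlation and 10% inflation.

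**The concern.** When allocation is balanced within a factor and the analysis leaves that factor out, any outcome variation it explains still counts as error, even though it hardly affects the difference between arms. The standard error is then overstated and the test runs a little below its nominal level.

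Here the factor is clinical site. Site variation in change could come from drift in test administration, staff turnover or practice effects that differ between sites. The month-of-visit term takes out only a learning effect common to everyone, and area takes out only differences between areas. What remains is variation between sites within an area. At stake is some precision in the QNPZ-8 comparison and in the other linear comparisons built the same way.

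**Working it through.** **Inputs from section 8.2.2.5.** Difference 0.13; SD of change 0.7; exchangeable correlation; follow-up visits at months 4, 8, 12, 24, 36 and 48; 80% power; 5% level, taken as two-sided; N 550, inflated to 605 and planned as 600.

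**Assumed, because the documents do not give it.** The within-area, between-site ICC of a participant's mean change, shown from 0 to 0.10. For the simulation: 20 or 55 sites, five areas (the main trial's regions) and an exact half split within each site.

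**1. Reproduce the plan's figure.** Under exchangeable correlation the variance of the mean change over m visits is v = SD² × (1 + 1/m)/2.

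- m = 5: v = 0.49 × 0.6 = 0.294. The two-sample t calculation gives exactly 550 and matches all 12 cells of Table 3. 550 × 1.1 = 605.
- m = 6: v = 0.49 × 0.5833 = 0.2858, giving N = 534, within 3% of 550.
- Power at a difference of 0.10 with 600/1.1 ≈ 545 evaluable is 57.6% (m = 5) or 58.8% (m = 6), against the stated 58%.

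The plan's figures reproduce. The steps below use m = 5 and n = 550.

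**2. Effect of leaving site out.**

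- SE reported by the area-only model: √(4v/n) = √(4 × 0.294/550) = 0.0462; half-width 1.96 × 0.0462 = 0.0906.
- True SE when arms are balanced within site: 0.0462 × √(1 − ICC). A model with site reports this SE.
- Size of the area-only test: 2Φ(−1.96/√(1 − ICC)).
- Power, area only: Φ[(0.13 − 0.0906)/(0.0462 × √(1 − ICC))].
- Power, with site: Φ[0.13/(0.0462 × √(1 − ICC)) − 1.96].

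| ICC | Half-width, area only | Half-width, with site | Excess width | Power, area only | Power, with site | Gain (points) | Size, area only |
|---|---|---|---|---|---|---|---|
| 0 | 0.0906 | 0.0906 | 0% | 80.27% | 80.27% | 0 | 0.050 |
| 0.01 | 0.0906 | 0.0902 | 0.5% | 80.39% | 80.66% | 0.27 | 0.049 |
| 0.02 | 0.0906 | 0.0897 | 1.0% | 80.51% | 81.06% | 0.55 | 0.048 |
| 0.05 | 0.0906 | 0.0883 | 2.6% | 80.88% | 82.24% | 1.36 | 0.044 |
| 0.10 | 0.0906 | 0.0860 | 5.4% | 81.53% | 84.22% | 2.69 | 0.039 |

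With m = 6 the gains are much the same: 0.26, 1.30 and 2.58 points at ICC 0.01, 0.05 and 0.10.

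**3. Simulation** (1,500 runs per setting; site entered as fixed effects). Mean SE fell from 0.0456 to 0.0447 (20 sites of 28, ICC 0.05) and from 0.0461 to 0.0438 (55 sites of 10, ICC 0.10). With no true difference, the area-only test rejected in 3.8% to 5.2% of runs; the Monte Carlo error is √(0.05 × 0.95/1500) ≈ 0.6 points. So the area-only test was at or slightly below its nominal level.

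**The case against.** The case for leaving the model alone is strong on size.

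- **Nothing in the documents shows a material site effect on change.** The endpoint is change from the participant's own baseline, so stable differences between sites in tester, language or level cancel. Section 8.2.2.4 matches norms to age, education, sex and race/ethnicity, not to site, and section 8.2.3.1 has the z-scores calculated centrally. A reader might take the limit on sites and the monitoring for re-training as an admission that sites differ. These are controls that should make the ICC small; they do not show that a large one remains. This stands.
- **A reader might infer that power already paid for is lost.** The documents do not support that. The SD of 0.7 is a total SD, so site variation is already inside it, and the sample size takes no credit for site adjustment. Section 8.2.2.5 also describes 0.7 as a conservative choice against 0.52 observed in SMART, although a second study did observe 0.7. The sample size is to be recalculated, with the pooled SD monitored for that purpose. This stands.
- **Within-site balance is approximate.** Section 3.4 gives no block size, and only a high proportion of eligible participants is to co-enrol. The table assumes exact balance, so it is somewhat favourable to adding site.
- **Area-only stratification matches the main trial's Cox model** (section 5.1), so it may be deliberate, and it is valid. But the sparse strata that many sites would create in a stratified Cox model do not arise with a random intercept in a linear model.
- **No separate analysis plan for the Neurology substudy is among the documents**, and such a plan could add the term. Section 8.2.4.1 does, however, name the model's stratification and covariate, so the term belongs there or in a plan that refers to it.

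**Conclusion.** The point holds as a minor loss of efficiency. The allocation is made within site, the primary model adjusts for area and month of visit, and any within-area site variation in change is left in the error. The interval is then conservative by about 0.5% to 5.4%, and power at 0.13 is about 0.3 to 2.7 points below what a site-adjusted model would give, for assumed ICCs of 0.01 to 0.10. At ICC 0 there is no loss.

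The treatment estimate is unbiased, the type I error is not inflated, and the planned 80% power is met without the change. The size rests entirely on an ICC that the documents do not supply. A reader might also want a site term in every substudy model. That does not follow: the binary impairment comparison (GEE is the plan's example) and the ordinal ADS model would then estimate a different, site-conditional effect, and the binary model with fixed site effects would risk sparse cells.

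**What to change.** In section 8.2.4.1, pre-specify a random intercept for clinical site, nested in geographical area, in the linear mixed models for QNPZ-8, the component test scores and CES-D, with change from baseline as the response so that the term captures site differences in change. Keep geographical area and month of visit as planned. Leave the impairment and ADS models as they are.

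The cost is one term in the model statement, using a variable already recorded for everyone: no new data, no new participants, and essentially no loss if the site ICC is zero. It should be fixed before unblinding, because adding site afterwards would look data-driven.
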